Principal investigator is the qualified person responsible for the conduct of the clinical trial in the research center.

Monitoring is the activity related to the supervision of the course of the clinical trial, in order to make sure that a given investigation is carried out and recorded, and the report is produced in accordance with the trial protocol, documented procedures, set standards and applicable regulatory requirements.

Multicenter studies are clinical studies which are conducted according to a unique protocol in two or more research centers.

Commissioner (Sponsor): An individual or organization bearing responsibility and having duties regarding the initiation or conduct of the clinical trial. For this trial, the Sponsor is the «Becton Dickinson and Company», Russia.

Case report form, CRF: A set of documents in the form of a hard copy, electronic or optical data carrier recorded for each study subject, which, according to CT protocol, contains information that must be submitted to the study sponsor.

Investigator (same as physician-investigator): The individual member of a research team appointed by and subordinate to the Principal Investigator in the research center, who will carry out the major procedures related to the clinical trial or take important decisions pertaining to all aspects of the clinical trial.

Research center (Center): An institution or site where the clinical trial is conducted.

Clinical trial: Systemic study with participation of one or more individuals as study subjects, aiming at evaluating the safety or functional characteristics of a medical device.

Outcome measure (primary): The most important parameter(s) used to test the main hypothesis in the clinical trial.

Outcome measure (objectives) (secondary): Parameter(s) used to test additional hypotheses in the clinical trial.

Adverse Event (AE): : Any unfavorable medical manifestation, such as an unanticipated disease or trauma, as well as undesirable clinical signs, including abnormal laboratory values, in the subject, user, or any other individual who may not be associated with the studied medical device.

Unanticipated Adverse Device Effect (UADE): Undesirable effect associated with the use of studied medical device.

Serious Adverse Event (SAE)is

An SAE is any AE occurring during study participation that results in any of the following outcomes:

a) leads to a lethal outcome;

b) leads to the serious deterioration of the health of the subject, which, in turn, leads to either:

- 1) disease or a life-threatening injury, or
- 2) injury, or
- 3) hospitalization or its extension, or
- 4) medical or surgical intervention for the prevention of the life-threatening disease or injury;

c) fetal injury, fetal death or abnormalities or defects of fetal development.

Unanticipated Serious Adverse Device Effect (USADE): Serious unfavorable effect of the device, of which the character, extent of effect, severity or consequences of its use have not been identified in the current working version of the risk analysis report.

Deviation: Case(s) of departure, deliberate or accidental, from the protocol requirements.

Clinical trial design (study protocol): The document which states the substantiation, objectives, study proposal (plan) and prospective analysis, method, monitoring, management and maintenance of the records pertaining to the clinical trial.

Procedure of obtaining the informed consent: The process during which the subject is provided with complete information about the clinical trial, and he/she gives a voluntary consent for participation in the clinical trial.

Sensitive subject is an individual whose preparedness to participate in the clinical trial can be unduly affected by anticipation, reasonable or not, participation-related benefit or negative reaction of the administration in case of the subject's refusal to participate.

Objective means the main objective of the clinical trial.

Ethics committee; EC: An independent committee responsible for the analysis of the clinical trial aiming at protecting the rights and ensuring the safety and wellbeing of the subjects taking part in the clinical trial.

Brief description of the clinical trial

Title	The role of proper insulin injection technique in the treatment of diabetes mellitus
Type	A prospective, post-marketing, single-arm clinical study
Duration	Planned First patient in: end of June 2019 Enrolment period: approximately 1 month Study duration per patient: 6 months
Number and name of research centers	
Total number of centers - 6:
 
 1. Federal State-Funded Institution “National Medical Research Center of Endocrinology” of the Ministry of Healthcare of the Russian Federation. 2. State-Funded Healthcare Institution of the Moscow Region “Moscow regional clinical scientific research institute named after M.F. Vladimirsy (MONIKI)”. 3. State-Funded Healthcare Institution “Endocrinology Dispensary of the Health Department of Moscow City”. 4. Federal State-Funded Educational Institution of advanced professional education of the Russian Medical Academy of continuous professional education of the Ministry of Healthcare of the Russian Federation. 5. State-Funded Healthcare Institution of the Sverdlovsk region “Sverdlovsk regional clinical hospital №1”. 6. Pavlov First Saint Petersburg State Medical University
Rationale	Insulin is the drug used in the treatment of diabetes mellitus, and it is administered via injection into subcutaneous adipose tissue. Proper technique of insulin injection in diabetic patients is a prerequisite for achieving good glycemic control, a reduction in the variability of insulin absorption, and reaching optimal efficacy of the anti-diabetic drugs [1].
Objective	The study aims at testing the effect of training in optimal technique of insulin injection using a multimodal individual approach supplemented with a platform for personalized distance education of diabetic patients who are on insulin therapy, with regard to clinical outcomes and essential skills necessary for managing diabetes.
Outcome measures	
 - Reduction in glycated hemoglobin (HbA1c) (in %); - Insulin total daily dose (TDD); - Incidence of hypoglycemia;

	
 - Incidence of severe hypoglycemia (which required assistance by others); - Change in Blood Glucose levels (measured by BGM) - Correct alternation of injection sites; - Cases of repeat needle use; - Changes in lipohypertrophy, its size (length and width, in mm) and localization (if applicable); - Cases of injection into lipohypertrophy areas (if applicable); - Quantitative experience with the use of distance-learning video lessons by patients. - Quality of Life assessments
Number of participants	At least 73, but not more than 90.
Length of time of patients' participation	
Total time of patient participation in the study is 6 months, which includes:
 
 - Three personal visits - Two phone calls
Selection criteria	
Selection of patients will not be influenced by race, religion, socio-economic and other factors. Approximately 50% of the subjects to be enrolled will have lipohypertrophy areas and 50% of the subjects will not.
 
Inclusion criteria:
 
 1. Type 1 or type 2 diabetes mellitus; 2. Patients (male and female) of 18 years of age and over; 3. At least 1 year of experience with insulin self-administration; 4. Use of insulin pen for insulin injections. 5. HbA1c > 7.5 % measured at study entry or maximally 30 days prior to screening. 6. BMI below 40 kg/m² at study entry. 7. Daily self-control of blood glucose level; 8. Access to the internet for watching video lessons. 9. Only outpatients are eligible for the study. 10. Availability of signed informed consent of the patient for inclusion in the study. 
Exclusion criteria:
 
 1. Pregnant women or women planning to become pregnant during the time of study, breastfeeding women; 2. Subjects using an insulin pump; 3. Those using treatment with a GLP-1 receptor agonists alone; 4. Subjects not fluent in Russian (reading and writing). 5. Patients at high risk for ketoacidosis and/or hyperglycemia. 6. Psychic, physical or any other reasons hampering patient participation in the study (based on the reasonable opinion of the physician-investigator).
Name of medical	Disposable BD Micro-Fine Plus 32G pen needle (0.23 x 4 mm).

device and its manufacturer	Manufacturer: "Becton Dickinson and Company", USA.
Ancillary Products	Blood Glucose Meter
Interim analysis	Will not be carried out.
Statistical analysis	
The HbA1c and insulin total daily dose will be analyzed using linear models with mixed effects (with transformation or without it, whenever necessary) where lipohypertrophy will be a fixed effect. Analyses will be done overall and per lipohypertrophy sub-group (with or without LH) whenever the sub-group effect is significant. Generalized linear models with mixed effects will include logistic models for binomial responses or Poisson models for count responses.
 
Fixed effect models can be used when models with mixed effects cannot be employed. The effect of different covariates will be studied (including, but not limited to these), such as site, age, BMI, gender and diabetes type, as well as their interaction. The threshold to keep covariates in a model will be $p < 0.05$.

1. Identification and description of the medical device used in the trial.

Disposable BD Micro-Fine Plus 32G pen needles (0.23mm/32G x 4mm) will be used. The needles (Fig. 1) are made of stainless steel AISI 304, silicone, UV light curable adhesive, polypropylene, polyethylene and paper/copolymer film. The length of the needle is 4 mm, diameter 0.23 mm and weight 3 g.

BD Micro-Fine Plus 4 mm 32G needles are intended for parenteral (subcutaneous) injection of medicines (insulin, hormonal medications and other drugs supplied in cartridges which, in turn, are enclosed in pen injectors [pre-filled syringes]).

BD Micro-Fine Plus 4 mm 32G needles are intended for self-injection of medications by the patient at home, using special injectors (pen injectors or pre-filled syringes). The same needles can be used in the hospital by skilled medical staff, provided the cartridges and injectors are used individually for each patient.

The needles are manufactured by the «Becton Dickinson and Company», USA. The manufacturing sites include [name], and [name].

Fig. 1 Disposable BD Micro-Fine Plus 4 mm 32G needle (0.23mm/32G x 4mm): view of the open needle, individually packaged and in a carton box.

2. Study sponsor

The study is sponsored by the «Becton, Dickinson and Company», Russia. Becton, Dickinson and Company is a manufacturer of different medical devices, including needles for insulin pen injectors. The company provides all necessary educational, instructional and supporting materials and provides assistance with the monitoring of studies, the analysis of data, and the publication of results.

For the period of the clinical trial, BD supplies all participating patients with 4 mm 32G needles free of charge.

In the course of study, the required number of needles (depending on the number of insulin injections per patient and the number of patients in every center) will be supplied by the Sponsor to the research center. An entry will be made regarding the supplied needles (number of packages, date of receipt, batch №) by the investigator in a special log book (see Appendix A to the protocol). Upon study completion, the center must return all unused needles (if any) to the Sponsor and mark this in the needle log book.

The needles will be used for insulin injection by patients with type 1 and type 2 diabetes mellitus who have been using insulin injections for more than a year. The injections will be done using pen injectors.

BD will also supply, via the research center, a Blood Glucose Meter (BGM) as well as sufficient lancets and test strips to all study patients for use in the study. This BGM will need to be returned to the research center after the patient finished the study. This will also be documented in a log book. Upon study completion, the center must return all BGMs (used and unused) unused strips and lancets (if any) to the Sponsor and mark this in the corresponding log book.

3. Rationale of clinical trial plan (design)

To date, several clinical trials have been conducted [2,3,4] with the aim of evaluating the effect of proper insulin injection technique on such parameters as glycemic control, glycated hemoglobin, hypoglycemia, glycemic variability and TDD of insulin. The above mentioned studies attest to the fact that the use of proper injection technique yields tangible results, namely, a reduction in % of glycated hemoglobin, an improved control of blood glucose level and an overall improvement of patient satisfaction with treatment. A 6-month follow-up is considered a necessary and sufficient measure for the evaluation of the above parameters. In our study, we would also like to evaluate all the above mentioned parameters with regard to proper injection technique; in addition, physicians' explanations on the injection technique will be reinforced by on-line video lessons, which will be recommended by the attending physician to patients for their own viewing.

4. Summary about the training and experience of the medical staff needed to handle the device

The experienced medical staff participating in this trial are in a position to handle the insulin pen needles. However, the Sponsor will run training classes for the medical specialists involved

in the study to familiarize them with the study protocol, including a briefing on how to find lipohypertrophy areas (using training phantoms). Training will employ the “teach the teacher” method. Moreover, the Sponsor will run training classes on how to fill in the supporting documents required for the clinical trial, such as source worksheets, and the eCRF, the needle log book, etc. The site staff will also be instructed on how to deal with the subject diaries and how to administer the Quality of Life questionnaire EQ-5D.

5. Risks and benefits associated with the use of the device and the clinical trial

The risks associated with the use of disposable BD Micro-Fine Plus: 32G (0.23 x 4 mm) needles and the injection pen are the standard risks occurring during subcutaneous injections, which include the following:

- 1) *Hemorrhages and hematomas.* Sometimes during an injection, the needle may damage blood vessels, causing hemorrhages or hematomas. Changes in needle length or other injection parameters do not seem to influence the rate of occurrence of bleeding or hematomas, although, according to some data, these complications may occur less frequently when short needles are used. Pressing on the injection site for 5-10 seconds should stop the bleeding [1].
- 2) *Leakage of the medication from the injection site.* This can occur due to the following reasons:
 - a) a one-time injection of a large insulin dose. In some cases, it would be preferable to divide large insulin doses into two doses and inject them one after another [1].
 - b) individual skin properties (dermal structure) and its age-related changes may be the cause of medication leakage following an injection [1].
- 3) *Pain.* Injections of insulin and GLP-1 receptor agonists do not usually cause pain, except for cases when the needle damages nerve ending fibers, which is a fairly rare event. However, some patients respond to injections in a rather sensitive way and describe their sensations as painful ones. Patient discomfort during injections was carefully studied and is attributed to three key factors: needle length, needle diameter and injection setting [1].

The benefit provided by this study is the demonstration of the fact that proper insulin injection technique used by patients is a prerequisite for achieving good glycemic control of diabetes, reducing the variability in the absorption of insulin preparations, and obtaining the optimal effect of their use [1]. Also, we expect that the proper technique of insulin injections will help to reduce the risks of injections: hemorrhages, hematomas cases and pain.

6. Objectives of the clinical trial and the hypotheses to be tested

The study aims at verifying the effect of teaching the optimal technique of insulin injection using the multimodal individual approach, supplemented with a personalized remote platform for the education of diabetic patients who are on insulin therapy, with regard to the clinical outcomes and essential skills necessary for managing diabetes.

This is a prospective study conducted in Russia, with a subsequent progress review after a 6-month follow-up to assess the correctness of insulin injection technique. The study design represents a “before” and “after” comparison, where the patient is left under

his/her own control after the health worker-guided assessment of the existing technique, and is undergoing training in conjunction with the reinforcing video lessons. The study includes patients with and without lipohypertrophy. During the follow-up phase, the insulin total daily dose, extent of glycemic control (glycated hemoglobin, hypoglycemic episodes), repeat use of needles, insulin injection technique and practical use by patients of the taught hands-on skills will be reviewed and evaluated.

Hypothesis

- Proper insulin injection technique, which includes the single use of needles, alternating the injection sites, avoiding injection in lipohypertrophic areas and the use of short (4 mm-long) needles will allow us to improve glycemic control parameters (% glycated hemoglobin, hypoglycemia) and to reduce insulin TDD .

Primary objective

- Evaluation of the effect of personalized teaching of the optimal insulin injection technique in conjunction with the use of disposable BD Micro-Fine Plus 32G (0.23mm/32G x 4 mm) pen needles on the reduction in glycated hemoglobin (HbA1c in %) after 6 months follow up in patients with Type 1 or Type 2 diabetes .

Secondary objective

- Evaluation of the effect of optimal insulin injection technique on the total daily dose of insulin and clinical parameters of glycemic control (hypoglycemia and severe hypoglycemia requiring third party assistance).
- Evaluation of the effect of optimal insulin injection technique on glucose blood levels (measured by BGM).

Additional objective

- Evaluation of the effect of education (especially distanced learning) on patients' knowledge and their mastering insulin injection technique, including correctly alternating the injection sites, avoiding injecting the lipohypertrophy areas, and the single use of needles.

7. Clinical trial proposal (design)

This clinical trial is a prospective, post-marketing, single-arm clinical trial.

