7.4. Patient information and obtaining informed consent

Before executing any study procedure, the informed consent of the patient must be obtained. The following steps must be taken in order to obtain the informed consent of the patient for participation in the study.

1. Physician-investigator must ascertain whether patients understand and read Russian.
2. Patient receives information about the study, its objectives, a brief description of the study design and the patient requirements in case he/she consents to participate in the study. Patients are informed that they meet the criteria required for study entry.
3. Patient takes his/her time to ask questions, discuss the study with family members and take a decision about study participation before the next visit to the medical center. If the patient gives his/her consent to participate in the study, the next visit is scheduled within 5 days from the moment of signing the informed consent form by the patient.
4. Patients are informed that they are entitled to change their mind and withdraw from participation at any time, and this will not affect their treatment in any way.

A patient is considered to be enrolled in the study when he/she signed the Informed Consent Form.

7.5. Stages of the clinical trial.

The enrolment period of the trial will be approximately 1 month, The follow-up period for each patient is 6 months. A total of maximally 90 patients will be included in the trial, to allow for 73 evaluable subjects at 6 months follow up, which is due to the statistical calculation of the required number of patients (see section 10 of this protocol).

The study design and calendar of events, including all the necessary visits, their order, appointment time and manipulations carried out during the visits, are presented in Fig. 2 (Study Flow) Table 1 (Study design) and Table 2 (Calendar of events).

[figure not shown]

Fig. 2. Study Flow

Table 1. Trial design

Patient selection and start		Interim control (telephone)	Interim control (3 month FU visit)	Completion and evaluation
Visit 1 (Screening) duration - 5 working days	1 Patient evaluation in terms of his/her possible participation in the study. For female patients: perform a pregnancy test	1 Make sure that patient follows study protocol: uses supplied needles only once, and watches recommended video lessons	1 Enter data regarding HbA1c and insulin TDD	1 Enter data regarding HbA1c and insulin TDD

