	2 Obtaining the informed consent	2 Evaluate current level of glycemic control and cases of hypoglycemia	2 Evaluate current level of glycemic control and cases of hypoglycemia.	2 Evaluate current level of glycemic control and cases of hypoglycemia.
	3 Assignment of participant identification number (code)	3 Find out about current level and frequency of measuring blood glucose and insulin TDD.	3 Examine injection sites and injection technique, size and localization of lipohypertrophy	3 Examine injection sites and injection technique, size and localization of lipohypertrophy
	4 Fill in the questionnaire, enter data regarding HbA1c and insulin TDD. Note: the HbA1c value may be measured at screening or the latest measured value (max. 30 days prior to screening) may be taken.	4 Make sure that the patient follows the recommended injection technique, correctly alternates injection sites and avoids injections into sites of lipohypertrophy. Remind the patient to use the BGM and complete the diary.	4 Enter data regarding possible AE	4 Collect diary and review completion
	5 Examine injection sites and injection technique, size and localization of lipohypertrophy (if applicable).	5 Enter patient's answers in the interim control form	5 Review diary completion	5 Request patient to complete the EQ-5D questionnaire
	6 Evaluate current level of blood glucose and cases of hypoglycemia.	6 Remind patient about next personal visit	6 Download the data from the BGM to a PC for further statistical analyses.	6 Arrange subsequent medical follow-up for the patient, if required
	7 Carry out personalized training on correct injection technique	7 Enter data regarding possible AE	7 Provide new supply of BD Micro-Fine Plus 4 mm 32G needles (3 months' supply) and additional strips and lancets for BGM.	7 Release patient from participation in the study (fill in Exit from study form).
Follow-up visits – visit №2, and 4 (by phone) in 45 and 135 days +/-10 days after visit 1		Follow-up visit – visit №3 (personal) in 90 days +/-10 days after visit 1		Visit 5 (personal, final) in 180 days +/-10 days after visit 1

8 Familiarize patient with distance education resource and recommend independent studies using video lessons		8 Schedule the HbA1c test and next personal visit in 90 days. Schedule next telephone follow up (visit 4)	8 Download the data from the BGM to a PC for further statistical analyses.
9 Request patient to complete the EQ-5D questionnaire			9 Enter data regarding possible AE

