7. A theoretical course is given on lipohypertrophy and the necessity of alternating the injection sites, followed by hands-on classes on insulin injection technique. Also, patients are familiarized with other aspects of insulin therapy. Patients are given instructions that, in case of necessity, they can change the insulin dose during the clinical trial. The patient is not recommended to change the long-acting and intermediate-acting insulins, and not to change insulin subgroups, i.e., short-acting and ultra short-acting insulins.
8. The patient is familiarized with the structure and scope of the distance learning program. The whole course of video lessons will be recommended to the all patients for individual studies independently from their insulin injection technique success.
9. Patients are requested to complete the EQ-5D questionnaire, see Appendix B for an example.
10. Patients are supplied with an information package – booklet with instructions how to practice the right injection technique, rotation grid, the information letter for a physician in a local outpatient hospital to inform the patient is participating in the clinical trial. The letter should be formalized on the formal paper of the site. Guidelines on video lessons and web access codes, if required.
11. Patients will also receive:
 - a. disposable BD Micro-Fine 32G (0.23mm/32G x 4 mm) needles in the amount

required for 3 months (Table 3),

- b. Blood Glucose Meter (BGM), strips and lancets in the amount enough for 400 measurements, which corresponds with 100 days (approx. 3 months) of 4 measurements per day,
- c. a patient's diary. Patients are requested to record their insulin doses and if they experienced any adverse effects, including hypoglycemia's.

12. Patients must be informed to return the BGM back to the site after the study. Boxes of needles, boxes of strips and lancets will be marked: "BD property. Only for clinical trial. Not for sale". Glucometers will be marked: "BD property. Only for clinical trial. Not for sale. Must be returned".

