In 1 week +/- 2 days after the visit № 1, the investigator must be sure that the patient has viewed the recommended video lessons. To this end, the Sponsor provides the investigator with the report on the patient's use of the education resource. If the patient has not viewed recommended video lessons, then the investigator reminds him about the necessity of viewing the recommended video lessons. The information about video lesson viewing is marked in the patient's eCRF.

Visits № 2 and № 4- follow-up visits (over-the-phone visits, or personal visit).

1. The interim contacts with the patient are maintained over the phone in 45 +/-10 days and 135 +/-10 days from the first visit, with the view to evaluate the patient's adherence to the study design, review diary completion and to provide recommendations on the correction of the injection technique, as well as to evaluate the progress of his/her distance learning.
2. Information on the patient's glycemic control (glucose level), total daily insulin dose (the day prior to the phone visits) and hypoglycemic events since the last visit is requested and the information is entered in the eCRF.
3. To remind the patient to bring the BGM back on the next personal visit and to remind the patient on the appointment for having the HbA1c test, as was scheduled on the first and third visit
4. Data regarding possible AEs is collected in a special form of the patient's eCRF.
5. In case of the occurrence of adverse events (AE) in the course of the study after the screening visit, the investigator will record these in a special form (eCRF). In case of serious adverse events (SAE), the corresponding eCRF must be filled in and the event reported to the Sponsor and to the corresponding Ethics Committee within 2 working days after the investigator has become aware of the event.
6. The investigator has to remind the patient to measure their glucose levels upon the protocol requirements and complete the diary with insulin doses 2 weeks before the next personal visit. The same reminder will be also done 2 weeks before or even earlier the next personal visit.

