Quality of Life questionnaire (EQ-5D)	X			X
Patient examination for lipohypertrophy	X		X	X
Glycated hemoglobin (HbA1c)	X		X	X
Collect information on occurrences of hypoglycemia	X	X	X	X
Patient education classes, video lessons scheduling, provision of needles	X			
Control of video lessons' viewing	X	X	X	X
Exit from the study				X
Collection of adverse event information		X	X	X

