13.1. Adverse Event (AE) Management

At each study contact, subjects will be questioned in an open-ended manner regarding any new or worsening undesirable signs or symptoms they may have experienced since the previous contact. Elicited signs and symptoms must be comprehensively documented on the appropriate source documentation.

Each sign, symptom, disease or illness reported must be evaluated by the Investigator or designee to determine if it meets the definition of an Adverse Event.

The clinical course of the event will be followed according to accepted standards of medical practice until the event resolves, stabilizes, or in the opinion of the Investigator, is no longer considered clinically significant. The Investigator must supply the Sponsor with information concerning the follow up and/or resolution of the AE.

Some reported or observed signs and symptoms are inherent to subcutaneous injection and are likely to occur transiently for nearly all subjects in this study. Such signs or symptoms will **not** be considered AEs as long as they are mild (transient, easily tolerated, no interference with daily activities) and the Principal Investigator agrees. The following will not be **not** be considered AEs:

- Mild, self-limited pain, swelling at the injection site
- Mild bruising at the injection site
- Mild self-limited bleeding at the injection site

However, these signs and symptoms **must be considered AEs and** documented on the Adverse Event eCRF should any of them occur in such a way that the extent or nature of the experience exceeds that normally associated with the procedure, as judged by the Subject to be excessive pain, bruising or bleeding.

Some signs and symptoms are inherent to the conditions under study (i.e. diabetes) and are likely to occur transiently for nearly all subjects in this study. Episodes of hyperglycemia and hypoglycemia occurring after subject enrollment and exposure to study product and/or study procedures, should be reported based on the following criteria:

- All blood glucose values <2.8 mmol/L (hypoglycemia) or >22.2 mmol/L (hyperglycemia) that require 3rd party (defined as, assistance of another person to administer carbohydrates or glucagon) or medical assistance for recovery will be recorded as an AE and assessed for seriousness.

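### The protocol contradicts itself on when adverse event recording starts: Section 7.5 and its tables begin after the screening visit, while the definitions and Section 13 cover all of study participation, which begins at consent within that visit.

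*Protocol*

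**What the plan says.** Two sets of statements bear on the start of recording.

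**Later start.**
- Protocol Section 7.5, Visits 2 and 4, item 5: "In case of the occurrence of adverse events (AE) in the course of the study after the screening visit, the investigator will record these". The same item carries the duty to report serious events within 2 working days.
- Table 1 lists 13 steps for Visit 1, none of them for adverse events. Each later visit has such a step.
- In Table 2 the row "Collection of adverse event information" is blank under Screening and marked for Visits 2 and 4, 3 and 5.

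**Earlier start, or no limit.**
- The list of terms defines a serious adverse event over the whole of participation: "An SAE is any AE occurring during study participation that results in any of the following outcomes".
- Section 7.4: "A patient is considered to be enrolled in the study when he/she signed the Informed Consent Form".
- Section 13 says that all adverse events are recorded and gives no start date.
- Section 13.1: "At each study contact, subjects will be questioned in an open-ended manner regarding any new or worsening undesirable signs or symptoms". The question looks back to the previous contact.
- Section 13.1 dates reportable glycemic episodes from enrolment together with exposure to the study product or procedures.

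**What lies inside Visit 1.** Table 1 gives its length: "Visit 1 (Screening) duration - 5 working days". Consent is step 2, personalized training is step 7 and needle issue is step 10. The Visit 1 narrative describes a theoretical course "followed by hands-on classes on insulin injection technique" and an instruction that patients may change the insulin dose if necessary.

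**The concern.** A patient can be enrolled, trained and supplied with study needles while Visit 1 is still open. A site working from the visit schedule has no prompt to record an adverse event at that stage, and Section 7.5 tells it to start later. A site working from Section 13 would record the same event.

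The days in question may include the first use of the taught technique. Section 7.7 notes that patients who move from lipohypertrophic to healthy tissue often need less insulin to avoid hypoglycemia, so early events are of interest. With six centers, the adverse event list promised in SAP Section 7 could follow different rules at different sites. The SAP gives no start date that would settle the matter, and the handling of an early serious event would depend on which section a site followed.

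**Working it through.** The plan states no figure on this point, so the check is a comparison of the texts and a sizing of the window.

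**Step 1. When does participation start?** Section 7.4 says at signature of the consent form. Table 1 places consent at step 2 of Visit 1. Enrolment therefore precedes the end of the screening visit.

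**Step 2. When does recording start?**
- Section 7.5, Visits 2 and 4, item 5: after the screening visit.
- Tables 1 and 2: first entry at Visit 2.
- Section 13: all adverse events, no start given.
- Section 13.1, general: every study contact, and Visit 1 is one.
- Section 13.1, glycemic episodes: from enrolment and exposure.

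These cannot all hold for an event that occurs after consent but before Visit 1 closes. The late start is also more than one loose phrase, because the item and both tables agree with each other.

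**Step 3. Can time pass in that interval?** Yes. Table 1 allows 5 working days for Visit 1. Section 7.4 also schedules the next visit within 5 days of signing the consent form.

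**Step 4. How long is the window?** Five working days span 5 calendar days if they run Monday to Friday, and 5 + 2 = 7 if they cross a weekend. Against the 180-day follow-up:
- 5 / 180 = 2.8%
- 7 / 180 = 3.9%

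Both figures are upper limits for a patient, since they assume consent on the first day and use of the full allowance.

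**Step 5. Does later questioning close the gap?** Not reliably. The first scheduled adverse event step is at Visit 2, at 45 ± 10 days, which is day 35 to day 55. Section 13.1 asks there about the time since the previous contact. If that contact was the close of Visit 1, an earlier event falls outside the question. The optional one-week call lists only the check on video viewing.

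**Step 6. What is captured by other routes?**
- The diary issued at Visit 1 asks for adverse effects, including hypoglycemia.
- Table 2 marks collection of hypoglycemia information at Visit 1.
- SAP Section 5.2.5 summarizes five categories of hypoglycemia, including severe events needing third-party assistance.

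Hypoglycemia is therefore partly covered. Other adverse events have only the diary and Section 13.

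**The case against.** The best defense is that Section 13 is the dedicated safety section and should prevail over one item in a checklist for Visits 2 and 4. That item may only tell sites what to do at follow-up contacts. Section 13 records all adverse events, requires reports and sponsor forms for every serious one, and has no exclusion for screening. This is a fair reading, but the protocol does not say that Section 13 takes precedence, and both tables follow the later start.

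A reader might infer more than the documents support, in four ways:
- *That events in these days go unrecorded.* Section 13 and the diary can capture them. What the text shows is uncertain capture, not a settled exclusion.
- *That a serious event in the window would have no form.* Section 13 requires one, so the most that can be said is that a site following Section 7.5 might not complete it.
- *That the adverse event list is the only safety output.* SAP Section 5.2.5 covers hypoglycemia and Section 6.4 lists device failures. Under Section 13.1, hypoglycemia that resolves with standard carbohydrate is by default not an adverse event, so an extra entry step would not collect most such episodes.
- *That 90 × 7 = 630 patient-days (630 / 16,200 = 3.9%, where 16,200 = 90 × 180) of exposure are lost.* That requires every patient to use the whole allowance, cross a weekend and consent on the first day. The documents do not say on which day training or needle issue occurs, or whether the needles are used before Visit 1 closes. Part of the window may precede exposure.

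It is also true that the primary endpoint, the sample size and the SAP's models are untouched.

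**Conclusion.** Wrong as written: an internal contradiction. The protocol gives incompatible starts for recording adverse events, and the latest of them falls after enrolment and after the training and needle-issue steps. Serious and non-serious events between consent and the end of Visit 1 may be entered at one site and left out at another.

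The window is at most 5 working days per patient. The conclusion assumes that Visit 1 can extend over more than one day after consent, as Table 1 and Section 7.4 allow, and that sites may work from the visit schedule. It does not assume that any event has been or will be lost. The share of the window that follows first exposure cannot be determined from the documents. The consequence is limited to the completeness and between-site consistency of the safety data.

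**What to change.** State one start for recording both adverse events and serious adverse events: signature of the informed consent form, which is already the protocol's enrolment point. Then:

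1. In Section 7.5, Visits 2 and 4, item 5, replace *after the screening visit* with *after signature of the informed consent form*.
2. In Table 1, add an adverse event entry step at the end of Visit 1.
3. In Table 2, mark the adverse event row under Visit 1.

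The cost is protocol wording, use of the existing adverse event page at Visit 1, and slightly more entries. No visit, treatment or analysis changes.
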